In this study we propose to use implementation science (IS) to scale up and evaluate the TXTXT evidence-based intervention (EBI) as an effective strategy to increase ART adherence and retention in HIV care, ultimately leading to a suppression of viral load among Black/African American, Hispanic/Latino and other racial/ethnic minority youth and young adults living with HIV (YYALH) participating in the intervention. We hypothesize that those who complete the TXTXT intervention will demonstrate a clinically meaningful increase in ART adherence, viral suppression, and sustained retention in care. Additionally, we hypothesize that the implementation of TXTXT will reach $\geq 80\%$ of the intended participants, will be fully adopted by $\geq 80\%$ of clinic partners, and will achieve $\geq 90\%$ ratings of satisfaction and acceptability. We will use mixed methods to complete our study aims: 1) determine the real-world efficacy of a regional scale up of an EBI – TXTXT -among poorly adherent racial/ethnicity minority YYALH, aged 16-35 years, on our primary outcomes: adherence and viral load suppression at 3-month post initiation of the intervention; and secondary outcome: retention in HIV care at 12-months post baseline, and 2) apply the Consolidated Framework for Implementation Research (CFIR) to describe the implementation process and identify barriers and facilitators needed to be addressed; and measure implementation outcomes of the TXTXT intervention using the RE-AIM framework (Reach, Efficacy, Adoption, Implementation, Maintenance). We will conduct a cluster randomized controlled trial to evaluate the intervention effectiveness (i.e., ART adherence, viral load suppression) at 3-months post-initiation of the intervention. Twelve clinic sites with the ability to enroll up to 50 participants at each site (N=600 participants total) will be trained to administer the TXTXT intervention. Sites will be randomized to either start the intervention immediately (i.e., intervention arm) or waitlisted to start at 3 months post baseline (i.e., comparison arm). In the comparison arm, the study will compare pre-post differences in adherence and viral suppression at 6 months post baseline. Last, we will evaluate retention in HIV care and sustained impact of the intervention at 12 months post baseline for all study participants.

RESEARCH TEAM

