The proposed research uses a cluster randomized controlled trial design to evaluate the effectiveness of TXTXT intervention on adherence and viral load suppression at 3 months post intervention initiation. A total of 12 clinic sites in the Midwest will be randomly assigned to either a 3- month observation period (i.e., comparison arm) or a 3-month intervention period (i.e., intervention arm). At the 3-month mark, sites randomized to the intervention arm will continue with the intervention for an additional 3 months, and sites initially assigned to the comparison arm will switch to the intervention for the 3 months. We will assess initial impact of the intervention by comparing the primary outcomes (i.e., ART adherence and viral load suppression) of the intervention arm to the comparison arm at 3-months post initiation of the intervention. This timepoint (3 months post baseline) was selected based on the findings of the randomized control trial used to establish efficacy of TXTXT.¹⁸ The study will also compare pre-post differences in adherence and viral load suppression for participants in the comparison arm at 6 months post baseline. Secondary outcomes of retention in HIV care and sustained impact of the intervention will be evaluated at 12 months post-baseline. At 3 months, 6 months, and 12 months post baseline, electronic medical record (EMR) data from participating clinics will be used to determine viral load and retention in care measures.

METHODS

Audience and Stakeholder Participation

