MATEC affiliated clinics in the Midwest region are eligible to participate in Aim 1 if meeting these criteria: (1) Clinic must have at minimum 40 current patients who are: racial/ethnic minority AND have a 'detectable' viral load AND are aged 16-35 years; (2) clinic must be willing to commit at least one staff person as lead for registering clients to receive the intervention, completing consent, and administering research surveys; (3) clinic must be willing to provide deidentified individual-level data for registered TXTXT participants, including viral load, retention in care (dates of clinic visits) at least twice per year; (4) clinic must not be using a competing medication reminder text messaging system; (5) clinic must be willing and able to rely on Lurie IRB. Once sites sign a memorandum of commitment, the study coordinator will schedule a conference call to conduct a standard of care questionnaire (Appendix K). The standard of care questionnaire will document existing clinic approaches to support adherence as well as any ancillary services (e.g., transportation assistance). This information will form a descriptive profile for each clinic.

Study Inclusion

For inclusion in the TXTXT intervention individuals must meet the following criteria: 1) diagnosed with HIV-infection and on ART regimen for at least one month (not new to ART); 2) aged 16-35 years; 3) have a viral load ≥ 200 c/mL and/or report poor adherence (<90% of pills taken in the last 30 days); 4) able to receive text messages; 5) provide informed consent for research component; and 6) are a patient of a participating clinic

Study Exclusion

Exclusion criteria includes: 1) those who are unable to give informed consent 2) those who are participating in other studies that impact primary and secondary outcomes.

Procedures for Recruitment and Informed Consent

Aim 1: Youth living with HIV (aged 16-35 years) who meet study inclusion criteria will be recruited by study staff from participating clinics. The EMR will identify potentially eligible patients who will be invited to complete further study screening and enrollment.

We will ask each clinic to construct a list of eligible patients and carefully track outreach, screening, and enrollment on an enrollment log provided. Clinics may enroll up to 50 participants (to account for 20% attrition, final sample of 40 participants per clinic).

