Retention will be facilitated through obtaining contact information for the participant during the initial stages of the enrollment process. To minimize participant and staff burden, the follow-up visits can be conducted virtually. Participants will be sent a personalized link to complete the follow-up survey via REDCap. Of note, there will not be financial reimbursement for participation in the

intervention as the goal of the project is to understand how TXTXT will work in the “real world” and inform wide scale routine implementation. Prior studies by Drs. [name], [name], and [name] with vulnerable adolescent and other marginalized populations have maintained >80% retention. We will employ best practices in participant retention including: 1) collecting extensive locator information (multiple addresses/emails, phone numbers, social media profile names, etc.); 2) identification and discussion of difficult-to-reach participants and potential solutions during weekly team meetings; and 3) maintaining flexibility with mode of follow-up (e.g., in person options as well as internet based). The investigative team and participating clinic staff will review the study team’s retention plans and will be asked for guidance on how to best keep YYALH engaged in the study for at least 6 months. No financial incentives will be provided to youth participating in the TXTXT intervention trial (Aim 1). At 3 months, 6 months, and 12 months post baseline, electronic medical record (EMR) data from participating clinics will be used to determine viral load; retention in care will be assessed for up to 12 months post baseline.

STUDY DESIGN AND DATA ANALYSIS

Study participation summary

1. 12 participating clinics randomized 1:1 into intervention or comparison arm
2. 50 participants at each clinic enrolled and complete baseline survey; baseline EMR data pulled
3. Participants at intervention clinics begin TXTXT after baseline survey and continue for 6 months
4. All participants complete a 3-month survey
5. Participants at comparison clinics begin TXTXT after 3-month survey and continue for 3 months
6. All participants complete a 6-month survey; 6-month EMR data pulled
7. TXTXT intervention stops at 6 months post baseline for all participants
8. 12-month EMR data pulled

Timepoint	Who	What	Data collected
zero	12 participating clinics	Randomized 1:1 intervention: comparison arm	

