The data manager and study coordinator will review the Dimagi platform data reports, which include logs of all texts sent, received, responded to, as well as a log of “STOP” requests. These reports will be pulled by week and by clinic. The data manager and study coordinator will provide summary data to clinic sites as well as action items (e.g., follow up with “STOP” participants to inquire if they would like to discontinue from the study, or stop their messages for short time period). Summary statistics will be provided monthly as process data for the entire study team to review.

Sites in the control arm will continue the standard of care, which will include traditional adherence counseling. Data from the EMR will be gathered for both the control and intervention site participants to include viral load and visit attendance.

At baseline, univariate analyses will be used to characterize the sample; and bivariate analysis will be employed to explore any differences between groups (e.g., differences between clinics; age categories; sex). Fisher’s Exact Test and χ^2 tests (for categorical variables) and t-tests (for continuous variables) will be used to identify demographic and behavioral factors associated with adherence and retention in care. Generalized linear models (GLMs) will be used to assess the effect of the intervention on the outcomes between the intervention and the control arm at 3 months and pre-post differences in the control arm after received the intervention at 6 months. GLMs can accommodate dependent variables with normal, binary, Poisson, and negative binomial distributions and can be adapted to incorporate random and fixed effects (generalized linear mixed models; GLMMs) to account for within-subject correlation among repeated measures over time.³¹ The generalized estimating equation (GEE) can be used to compare ‘average’ population-level response to the intervention.³² Potential confounding and effect modification by sociodemographic characteristics and location (defined by urban vs. rural residence) will be examined in exploratory analysis and these variables will be selected for inclusion in multivariable models based on statistical significance and conceptual importance. All models will account for correlation among repeated measures on individuals and within sites over time as appropriate. Inclusion of random effects for intercept and trend over time will be explored to assess subject-specific variability.

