In order to assess feasibility, acceptability and satisfaction of the intervention we will use descriptive statistics using a combination of objective (e.g., rates of participation, intervention completion) and subjective measures (e.g., reported satisfaction, acceptability). In order to characterize adherence and retention in care throughout the course of the study, Kaplan-Meier survival curves will be used to measure time to adherence and retention, and Cox proportional hazard ratios will be used to assess whether individual-level factors are associated with shorter mean time to outcome. To measure reach of the intended participants, we will compare the study sample to those available in the sampling frame (proportion of those enrolled to those eligible). To measure adoption of clinic partners, we will evaluate the number of clinic partners who propose to continue with text messaging as adherence support post study (proportion of clinics who propose to continue TXTXT post study to total clinics). Satisfaction and acceptability will be measured by standard quantitative scales, summary total scores will be evaluated to determine whether or not ≥90% ratings were achieved.

Outcome definitions

Medication adherence: greater than or equal to 90% on self-reported visual analog scaler (non-adherence categorized at less than 90%)

Retention in care³³: two visits 90 days apart in the past year will be considered retained in HIV care

Viral suppression³⁴: VL < 200 copies/mL will be considered virally suppressed

Sample size, power calculation, and clinic scale up

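### The 12-month retention measure looks back over the texting months, so it does not by itself show that retention is sustained after texts stop

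*Combined protocol and SAP*

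**What the plan says.** Retention in HIV care is the secondary outcome of Aim 1. Under Outcome definitions, "two visits 90 days apart in the past year will be considered retained in HIV care". The protocol gives no other definition of retention.

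The Aim 1 Research Design sets the time point: "Secondary outcomes of retention in HIV care and sustained impact of the intervention will be evaluated at 12 months post-baseline". The Protocol Summary hypothesizes that those who complete TXTXT "will demonstrate a clinically meaningful increase in ART adherence, viral suppression, and sustained retention in care".

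The Study participation summary fixes the exposure. Intervention clinics text from baseline to month 6. For the others, "Participants at comparison clinics begin TXTXT after 3-month survey and continue for 3 months". Then "TXTXT intervention stops at 6 months post baseline for all participants". The adapted texts include clinic appointment reminders (Appendix E), so they act directly on the visits that the outcome counts.

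Under Data Analysis Plan and Variables, effect models are named for outcomes "between the intervention and the control arm at 3 months and pre-post differences in the control arm after received the intervention at 6 months". The same section adds that "Kaplan-Meier survival curves will be used to measure time to adherence and retention".

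**The concern.** At month 12 the past year is the whole study period, with the texting months inside it. Nothing in the definition requires a visit after texting ends. Retention could look good at 12 months while attendance falls away once the reminders stop, which is what a claim of sustained retention has to exclude.

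No arm is untexted over the window either. The arms differ in exposure only in months 0 to 3. If someone compares the arms at month 12, the difference is a blend of early texted visits and later text-free visits, and it could be misread as evidence for or against durability.

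No other analysis in the plan fills the gap. The named effect models stop at 3 and 6 months. The Kaplan-Meier curves describe time to retention, not loss from care after month 6.

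**Working it through.** The plan states no figure for retention. Its only power table concerns 90% adherence at 3 months and plays no part here.

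**Step 1. Overlap of texting with the look-back (from the documents alone).**
- Look-back at month 12: months 0 to 12.
- Intervention clinics: texting in months 0–6, so 6 of 12 months.
- Comparison clinics: texting in months 3–6, so 3 of 12 months.
- Months 6–12 only: 0 of 6 months in both arms.

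**Step 2. Can the definition be met with no care after texting?** Yes. I read the rule as at least 90 days apart. Visits on day 1 and day 91 meet it, and 365 − 91 = 274 days without a visit may follow. At a comparison clinic, visits at months 0 and 3 can meet it before any text is sent.

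**Step 3. How much could this matter?** Assumptions, not in the documents: quarterly visits, each attended independently with probability p. Retained means at least two attended visits.
- All care ends at month 6, visits at 0, 3 and 6: 3p² − 2p³.
- Care continues, visits at 0, 3, 6, 9 and 12: 1 − (1−p)⁵ − 5p(1−p)⁴.
- Month-0 visit not counted, care ends at month 6, visits at months 1 and 4: p².
- Same, care continues, visits at months 1, 4, 7 and 10: 1 − (1−p)⁴ − 4p(1−p)³.

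| p | Care ends, 0/3/6 | Care continues | Care ends, 1/4 | Care continues, 1/4/7/10 |
|---|---|---|---|---|
| 0.5 | 50% | 81% | 25% | 69% |
| 0.7 | 78% | 97% | 49% | 92% |
| 0.9 | 97% | 99.95% | 81% | 99.6% |

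**Step 4. What would a 12-month arm difference mean?** Assume visits at months 3, 6, 9 and 12, base attendance b, and texting adds d, so q = b + d. The arms differ only at the month-3 visit (q against b). The arm difference is therefore d times the probability that exactly one of the other three visits is attended.
- Benefit vanishes at month 6 (later visits q, b, b): d × [q(1−b)² + 2b(1−b)(1−q)].
- Benefit lasts fully (later visits q, q, q): d × 3q(1−q)².

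For b = 0.5 and d = 0.2:
- Faded: 0.2 × (0.7×0.25 + 2×0.25×0.3) = 0.2 × 0.325 = 6.5 points.
- Lasting: 0.2 × 3×0.7×0.09 = 0.2 × 0.189 = 3.8 points.

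| b | d = 0.1: faded / lasting (points) | d = 0.2: faded / lasting (points) |
|---|---|---|
| 0.10 | 3.1 / 3.8 | 7.4 / 8.8 |
| 0.30 | 4.5 / 4.3 | 9.1 / 7.5 |
| 0.50 | 3.5 / 2.9 | 6.5 / 3.8 |
| 0.70 | 1.6 / 1.0 | 2.5 / 0.5 |

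The order reverses at b of about 0.26 for a 10-point effect and about 0.18 for a 20-point effect.

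**Step 5. A second model.** Simulated Poisson visits at 3 per year, with texting doubling the rate and no effect after month 6, give 12-month retention of 0.83 against 0.75. Applying the same two-visit rule to months 6–12 alone gives 0.18 in both arms. The spurious difference disappears, but two visits 90 days apart is a demanding rule for six months. That favours a one-visit rule for the post-texting period.

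**The case against.** The best defence is that the protocol never says the annual measure is the test of durability. The Research Design lists retention and sustained impact side by side, which can be read as two items. Sustained retention could simply mean staying in care over the year. Viral load at 12 months, after six text-free months, is available as a measure of lasting impact. Much of this stands. The annual definition is a reasonable description of a year in care, and 12-month viral suppression is untouched by the look-back. But the Protocol Summary names sustained retention as a hypothesis, viral load does not show visit attendance, and no other retention measure is defined.

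Three further points also stand:
- No between-arm model for 12-month retention is written, so Step 4 is a warning about a comparison someone may make, not a fault in a specified analysis.
- Step 3 takes an extreme, all care ending at month 6. It shows what the definition permits, not what is likely.
- A reader might infer that a faded benefit always gives a larger arm difference than a lasting one. The documents do not support that. They give no attendance rates, and under Sampling some participants are people being asked to re-engage in care, so the low attendance at which the order reverses cannot be ruled out.

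**Conclusion.** The point holds in a limited form. The texting overlap (6 and 3 of 12 months) and the fact that two visits by month 6 suffice follow from the protocol, given only that 90 days apart means at least 90 days. The annual measure therefore does not by itself show that retention is sustained once texts stop. The possible size (50%, 78% or 97% retained with no care after month 6) rests on an assumed quarterly schedule with independent attendance and a counted month-0 visit; without that visit it is 25%, 49% or 81%.

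The size of any 12-month arm difference does not reliably indicate durability. At base attendance of 0.3, 0.5 and 0.7, with 10- and 20-point effects, it is larger for a faded benefit; at low attendance it is smaller.

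A reader might go further and conclude that the trial can say nothing about lasting impact, or that its main result is compromised. Neither follows: the 3-month primary comparison does not use this measure, and viral suppression at 12 months is assessed after six text-free months in both arms. This is a cheap improvement to a secondary outcome.

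**What to change.** Keep the annual measure and label it a description of the year in care. Under Outcome definitions, add post-texting retention: at least one HIV care visit after month 6 and by month 12. Report it by arm, label it uncontrolled (both arms have been texted by then), and base any statement about sustained retention on it.

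If it is set beside the six months before baseline, state that regression to the mean may affect the comparison, because participants are selected for viremia or poor adherence and some after a lapse in care.

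Optionally, add a randomized comparison of at least one visit after baseline and by month 3. That is the only texted-versus-untexted contrast available for retention, and it says nothing about sustained effect.

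The cost is one or two definitions. Participating clinics must already be willing to provide "retention in care (dates of clinic visits) at least twice per year", so no extra participant visits are needed. The pre-baseline comparison, if used, needs a wider baseline EMR pull covering the previous six months of visit dates.

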yet?" and "Don't forget!" The SMS platform is bi-directional and has an automated response system, so the participant is able to answer "1=yes" or "2=no" in response (press 1 or 2). When participants respond affirmatively, they will receive an encouraging message such as, "Great job!" However, when they respond with a "no" they will receive an acknowledging and encouraging message such as "You can do it!" (Appendix E).

Participants will be asked to complete a self-administered online survey at baseline, 3 months and 6 months post baseline. The survey will be hosted on REDCap and can be taken on a computer, tablet, or mobile phone. Participants will have the option of completing the survey remotely or coming to the clinic and taking the survey on-site (at a computer or tablet provided by the clinic). The online survey will be taken by both the intervention and comparison arm. The survey will measure demographics, self-reported ART adherence, HIV medication self-efficacy, barriers and facilitators of adherence, acceptability of TXTXT, and satisfaction (Appendix F). The survey CASI will be pilot tested with a small number of participants and adjusted as needed. Participants will also be asked to consent to release of specific EMR data to include viral load and attendance at HIV care visits.

At all study visits, staff will use the Fidelity Checklist to structure the visit and make sure that all procedures are followed (Appendix G). All study visits reflect the following general structure:

1. Complete intervention assessment
2. Complete standard-of care adherence counseling
3. Complete TXTXT Personalization form
4. Enter information into Dimagi platform (see Dimagi training, Appendix B)
5. Schedule date of next appointment
6. Build general rapport
7. Thank them for participation

As part of the initial visit, basic ART adherence education should be provided, based on the practices and/or protocols at each site. For example, if a site does not have a standard practice for adherence counseling, at a minimum staff should review:

1. The current list of medications prescribed to each participant and how each medication should be taken (make sure they know how to take their prescribed medication).
2. In addition, basic facts on the importance of adherence should be reviewed with each participant, such as those described here:
<https://aidsinfo.nih.gov/understanding-hiv-aids/fact-sheets/21/54/hiv-medication-adherence>

Retention

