baseline	50 participants at each clinic	Participants at intervention clinics receive TXTXT	EMR data Baseline survey
		Participants at comparison clinics do not receive TXTXT (i.e., standard of care)	
3 months	50 participants at each clinic	Participants at intervention clinics continue with TXTXT	3-month survey
6 months	50 participants at each clinic	Participants at comparison clinics begin TXTXT TXTXT stops for all participants	EMR data 6-month survey
12 months	50 participants at each clinic		EMR data

Sampling

We will ask each clinic to construct a list of potentially eligible patients and carefully track outreach, screening, and enrollment on an enrollment log provided. Participants (N=600, n=50 per each clinic site) will be enrolled.

The list of potentially eligible patients will be constructed from available EMR data and will be queried based on: (1) diagnosed with HIV; (2) age range (16-35 years); (3) most recent viral load obtained in past 12 months. If potential participants meet the first two criteria, they will be evaluated based on (#3) viral load data. The following scenarios are possible: 1) potential participant is virally suppressed; 2) potential participant is viremic (>200 copies/mL); 3) potential participant does not have viral load data available. Patients who are viremic and meet criteria 1-3 (HIV status, age) will be considered eligible for study inclusion and will be called by clinic staff to confirm eligibility and assess interest. Patients who meet criteria 1 and 2 and are virally suppressed or missing viral load data will be contacted to assess eligibility - specifically, those who are virally suppressed will be queried about medication adherence (if <90% of pills taken in the past 30 days); for those who are missing viral load data they will be asked if they are willing to re-engage in HIV care and have labs drawn prior to enrollment (if so, they will follow steps outlined above for those with viral load

STUDY DESIGN AND DATA ANALYSIS

(VL) data). The list and eligibility assessment will be documented and reviewed on a weekly basis with individual sites to ensure timely enrollment into the study.

Data Analysis Plan and Variables

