A total of 12 clinics and up to N=600 YYALH will be enrolled in this study for evaluation purposes. Each clinic will be able to enroll up to 50 participants for a maximum total of 600 participants. We assume a 20% attrition rate, and therefore the sample size available for analysis will be N=480. Sites will be randomized to either a 3-month observation (i.e., comparison arm) or an immediate start intervention arm; at the end of the first 3-month period comparison arm sites will start the intervention for the 3 months and intervention sites will continue the intervention for an additional 3 months (6 months total). Pre-post EMR data, SMS data, and participant satisfaction data will be collected to determine efficacy, durability, maintenance and satisfaction (see expected outcomes). Rapid interim data analysis and interpretation will occur at 3 months. In Year 3, all clinics and participants (in both the initial control arm or intervention arm) will have their medical records abstracted. In addition, de-briefing interviews will be conducted with clinic staff to assess implementation outcomes. Final analysis and sustainability plan will be conducted and elaborated.

This cluster randomized control study is powered to detect 20% difference in ART adherence (>90%) among participants receiving the TXTXT intervention and the control groups. The power is calculated based on 3 levels hierarchical model design (i.e., randomization at the site level, two measures for each participant). The correlations between the participants within the site is assumed to be 0.05 and correlation within a participant is assumed to be 0.2. The proportion of participants with $\geq 90\%$ ART adherence for the control group is assumed to be 25%, 35%, 45% and 55%. The effect size is assumed to be 10%, 20% and 25%. Given Type I error rate is 0.05, using the mixed model approach, the corresponding power is listed below.³⁵ The sample size with 6 sites in each arm and 50 participants from each site would have 80% power to detect 20% difference at 3 month post baseline.

Table 2: Power (6 sites in each arm, 40 participants from each site)

		proportion of participants with $\geq 90\%$ ART adherence (Control)			
Effect Size	25%	35%	45%	55%	
10%	0.30	0.29	0.28	0.29	
20%	0.82	0.80	0.80	0.83	
25%	0.95	0.94	0.94	0.96	

Track Lessons Learned

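### The stated 80% power for a 20-point adherence difference at 3 months is not met by an unadjusted 3-month comparison, and the plan does not define a baseline-adjusted analysis that would support it

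*Combined protocol and SAP*

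**What the plan says.** The section on sample size, power calculation and clinic scale up (Aim 1) describes the model: "The power is calculated based on 3 levels hierarchical model design (i.e., randomization at the site level, two measures for each participant". It gives two correlations: "The correlations between the participants within the site is assumed to be 0.05 and correlation within a participant is assumed to be 0.2". It sets type I error at 0.05, control-arm adherence at 25%, 35%, 45% or 55%, and differences of 10, 20 or 25 points. The headline claim is "The sample size with 6 sites in each arm and 50 participants from each site would have 80% power to detect 20% difference", at 3 months after baseline. The table is titled "Table 2: Power (6 sites in each arm, 40 participants from each site)", and its 20-point row reads 0.82, 0.80, 0.80, 0.83.

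On timing, the recruitment and consent section states: "Participants will be asked to complete a self-administered online survey at baseline, 3 months and 6 months post baseline". The study participation summary adds "Participants at intervention clinics begin TXTXT after baseline survey and continue for 6 months" and "Participants at comparison clinics begin TXTXT after 3-month survey and continue for 3 months". At baseline, the timepoint table says "Participants at comparison clinics do not receive TXTXT (i.e., standard of care)".

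The Research Design section and the Data Analysis Plan both place the between-arm comparison at 3 months. The analysis plan names generalized linear models for it, mentions mixed-model and GEE versions as possibilities, and says repeated measures and site correlation will be handled as appropriate. It names no baseline-adjusted primary model and gives no degrees-of-freedom rule. Cluster autocorrelation appears in the abbreviation list, but no value is given anywhere.

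**The concern.** The power model uses two measures per participant, but only one adherence survey can show a difference caused by randomisation. The baseline survey is taken before any participant receives the intervention. The 6-month survey comes after the comparison clinics have had it for 3 months. If both measures in the formula are treated as outcomes that carry the full effect, the calculation uses information that the 3-month comparison does not have.

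The second measure could instead be baseline, used for adjustment. That is a legitimate design, but its power depends on how stable site-level adherence is between baseline and 3 months, and the plan is silent on that.

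The 80% is the main design property for the primary adherence outcome. If the true figure is lower, a null result would be read as stronger evidence of no effect than it is.

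**Working it through.** **Inputs.** From the sample size section: 6 sites per arm, 40 analysed per site (240 per arm), site correlation 0.05, within-participant correlation 0.2, type I error 0.05. Assumptions, because the plan does not state them: two-sided test, unpooled variance, and either a normal (z) or a t reference distribution. Results are listed for control proportions 25/35/45/55%.

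**Step 1: reproduce Table 2 with both measures carrying the effect.**
- Design effect = 1 + 2 × 39 × 0.05 + 0.2 = 5.10.
- Effective n per arm = 240 × 2 / 5.10 = 94.1.

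| Difference | Computed (z) | Table 2 |
|---|---|---|
| 10 points | 0.325 / 0.291 / 0.281 / 0.291 | 0.30 / 0.29 / 0.28 / 0.29 |
| 20 points | 0.837 / 0.804 / 0.804 / 0.837 | 0.82 / 0.80 / 0.80 / 0.83 |
| 25 points | 0.956 / 0.944 / 0.948 / 0.967 | 0.95 / 0.94 / 0.94 / 0.96 |

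Eleven of 12 cells agree within 0.02, and 6 of 12 agree at two decimals. With 50 per site the same formula gives 0.853/0.821/0.821/0.853 at 20 points and matches only 7 of 12 cells, so the table belongs to 40 per site.

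**Step 2: one measure at 3 months, no baseline adjustment.**
- Design effect = 1 + 39 × 0.05 = 2.95.
- Effective n per arm = 240 / 2.95 = 81.4.
- Power for 20 points by z: 0.781/0.745/0.745/0.781 (2 of 12 Table 2 cells matched within 0.02).
- By t with 12 − 2 = 10 df: 0.694/0.656/0.656/0.694 (0 of 12 matched).
- Difference detectable with 80% power: 20.50/21.37/21.31/20.43 points (z), 22.79/23.64/23.47/22.41 points (t).

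**Step 3: baseline as an adjustment variable.** Multiply the Step 2 variance by 1 − r², where r = (0.2 + 39 × 0.05 × CAC) / 2.95 and CAC is the site autocorrelation. CAC is an assumption and is varied from 0 to 1. The first figure in each pair is for 25% and 55% control, the second for 35% and 45%.

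| CAC | r | z, 20 points | t (10 df), 20 points |
|---|---|---|---|
| 0 | 0.068 | 0.783 / 0.747 | 0.696 / 0.658 |
| 0.5 | 0.398 | 0.847 / 0.814 | 0.766 / 0.730 |
| 0.7 | 0.531 | 0.897 / 0.870 | 0.828 / 0.794 |
| 1 | 0.729 | 0.979 / 0.969 | 0.948 / 0.930 |

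Reaching 80% in all four columns needs a CAC of about 0.44 (z) or 0.71 (t, 10 df). This reading fits Table 2 within 0.02 at a CAC of 0.35-0.40 by z (12 of 12 cells), or 0.7 by t with 10 df (11 of 12). A single site correlation of 0.05 that does not decay over time means a CAC of 1. There, none of the 12 cells match, and power is above the table.

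**Step 4: does the reference distribution matter?** In a simulation of an unadjusted test on 12 clinic means (beta-binomial data, 200,000 runs, no true effect), a 1.96 cut-off gave 7.8-7.9% type I error and t with 10 df gave 5.0-5.1%. The z figures are therefore optimistic for a trial of 12 clinics.

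**The case against.** The strongest reply is that the arithmetic of Table 2 is not wrong and that the plan never names an unadjusted 3-month test as primary. It describes two measures and a mixed model, so a shortfall in a test it did not choose shows no failure of its 80%. The double-credit formula is also not proven. By symmetry it gives equal power at 25% and 55% control in the 20-point row, whereas Table 2 prints 0.82 and 0.83. Baseline-adjusted readings fit at least as well: 12 of 12 cells by z at a CAC of 0.35-0.40, and 12 of 12 by t with 9 df at 0.7. With an undecayed site correlation, adjusted power is 0.93-0.98, better than claimed. The z shortfall is modest, at 4-6 points, and a site correlation of 0.04 instead of 0.05 would remove it. The larger drop comes from using t, which is a separate matter. Details may also lie in the reference cited for the method.

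Much of this stands. The mechanism behind Table 2 is an inference, and the trial may have more than 80% power. The baseline-adjusted range is illustrative, because it assumes equal outcome variance at both times while the entry criteria restrict baseline adherence.

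It does not rescue the claim. Each route to the table needs either an effect on a measure that cannot carry one at 3 months, or an autocorrelation that the plan does not give. The analysis plan commits to neither a baseline-adjusted model nor degrees of freedom.

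**Conclusion.** The concern holds. With 40 analysed per site, site correlation 0.05 and a two-sided 5% test, an unadjusted 3-month comparison has 0.75-0.78 power (z) or 0.66-0.69 (t, 10 df) for a 20-point difference, not 0.80-0.83. The chance of missing a true 20-point effect is then about 22-25% or 31-34%, against the stated 17-20%. With baseline adjustment, power may lie below or well above 80%, depending on a site autocorrelation, model and degrees of freedom that the plan does not state.

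This does not show that the trial is underpowered. It shows that the headline power does not belong to any analysis the plan defines. It should be fixed.

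**What to change.** Choose one of two routes.

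1. Recompute Table 2 for the single 3-month contrast, with 40 analysed per clinic and small-sample degrees of freedom for 12 clinics. Then restate either the power or the detectable difference.
2. Name a baseline-adjusted 3-month model as primary. Define the two measures, state and justify the site autocorrelation and the degrees of freedom, and show power over a range of autocorrelation.

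Under either route, reword the sentence that ties 80% power to 50 per site so that it says 50 enrolled and 40 analysed. This agrees with the Table 2 title, the 20% attrition assumption and the recruitment section.

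The cost is protocol wording and a recomputed table, with no extra participants. Under the first route the stated power may look less favourable. Under the second the team must commit to one primary model and defend an autocorrelation.
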